3.0 DESCRIPTIVE ENDPOINTS AND ADDITIONAL DATA

3.1 Baseline and Demographic Characteristics

The following baseline and demographic variables will be summarized for the subjects enrolled: gender, age, medical history, baseline echocardiographic measurements, etc.

3.2 Adverse Events

All the adverse device effects, serious adverse device effects, UADEs, USADEs will be summarized for all subjects who enrolled in this trial in terms the number of events, the percentage of subjects with events and event rate as # event/patient-month per MedDRA coding. Moreover, COVID-19 related AEs will be summarized in terms of number of events, the percentage of subjects with events per AE terms.

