5.4 Subject Enrollment and Registration

The subject is considered to be enrolled in the study upon signing and dating the informed consent form. Subjects will be considered registered upon femoral vein puncture for transseptal access in preparation for MitraClip System insertion.

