6.3 Subject Preparation

Prior to the MitraClip procedure, subjects must be assessed to ensure there is no significant change in the subject's overall condition (e.g., stroke, MI, active infection, endocarditis, hemodynamic instability, etc.) that would preclude treatment. If the subject has experienced any significant change that would preclude treatment, the subject must be treated and reassessed for the study. Such subjects are not considered registered.

Prior to the MitraClip procedure, baseline activated clotting time (ACT) must be determined following transseptal puncture for the MitraClip procedure. ACT and heparin administration (or alternative anticoagulation therapy) must be recorded.

Subjects must be prepared for the procedure as per the institution's standard practice for a percutaneous procedure, general anesthesia, and TEE.

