7.2 Device Relationship

Determination of whether there is a reasonable possibility that a product or device caused or contributed to an AE is to be **determined by the Investigator** and recorded on the appropriate source documents and eCRF form. Determination should be based on assessment of temporal relationships, evidence of alternative etiology, medical/biologic plausibility, and patient condition (pre-existing condition).

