7.3 Adverse Event and Device Deficiency/Device Malfunction Reporting

7.3.1 Adverse Event Reporting

All adverse events will be collected on each subject through the femoral vein puncture for transseptal access in preparation for MitraClip System insertion to the 1-year follow-up visit. Adverse events will not be collected for screen failure subjects.

The event course must be monitored until the event has subsided or, in a case of permanent impairment, until the event stabilizes and the overall clinical outcome has been ascertained.

Unchanged, chronic conditions and elective procedures (e.g., routine dental procedures) for a pre-existing condition are not considered AEs and should not be recorded on the adverse event page of the eCRF.

Non-cardiac related abnormal laboratory values will not be considered AEs unless:

- 1) the investigator determined that the value is clinically significant,
- 2) the abnormal lab value required intervention, or
- 3) the abnormal lab value required subject termination from the study.

Serious Adverse Event Reporting:

Serious adverse events, as outlined above, should be reported to the Sponsor, EC, and local Food and Drug Administration agency as soon as possible but no later than 24 hours from the site becoming aware of the event or as per the investigative site's local requirements if the requirement is more stringent than those outlined.

The date the site staff became aware of the SAE must be recorded in the source document. The Investigator will further report the event to the local GCP office and the Ethics Committee (EC) according to the institution's reporting requirements.

Serious adverse events, as outlined above, should be reported on the SAE Notification Form in the occurrence that the EDC System is not available. This does not replace the EDC reporting system. All information must still be entered in the EDC system once the system is back to normal function.

Study site	Reporting timelines
All Sites	Sites should report SAEs to regulatory authorities and the Sponsor no later than 24 hours from the day the site personnel became aware of the event or as per the investigative site's local requirements, if the requirement is more stringent than those outlined.

Sites must record the date the site staff became aware that the event met the criteria of an SAE in the source document. The Investigator will further report the SAE to the local EC according to the institution's EC reporting requirements.

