11.4 Electronic Case Report Form Completion

Site research personnel trained on the protocol and CRF completion will perform the primary data collection clearly and accurately based on source-documented hospital and/or clinic chart reviews. The investigator will ensure accuracy, completeness, legibility, and timeliness of the data reported to the Sponsor on the CRFs and in all required reports.

eCRF data will be collected for all subjects who are registered into the study.

Only authorized site personnel will be permitted to enter the CRF data through the EDC system deployed by the Sponsor. The Sponsor will use an electronic audit trail to track any subsequent changes of the entered data.

The following data elements will be collected on eCRFs:

Visit	Data Elements to be Collected
Screening	
- Document medical history- Weight, temperature, blood pressure and heart rate- MR severity, MVA and etiology (Functional or Degenerative) based on TTE/TEE- Left ventricular ejection fraction and left ventricular end-systolic dimension based on TTE- Mitral valve anatomy for MitraClip suitability
Baseline (within 14 days prior to subject registration)	
- Document medical history- Weight, temperature, blood pressure and heart rate- STS Mortality Risk Score for mitral valve replacement- EuroScore II- MR severity, MVA and etiology (Functional or Degenerative) based on TTE/TEE (screening TTE/TEE can be used if within 14 days)- KCCQ- NYHA Classification

Visit	Data Elements to be Collected
	
 - Pregnancy test for females of childbearing potential - Blood test (CBC with differentials and platelet count, serum creatinine, urea, CK and CK-MB, BNP and NT-proBNP) - Cardiac medications
Pre-Procedure (within 24 hours prior to subject registration)	
 - 12-Lead ECG - Weight, temperature, blood pressure and heart rate - ACT and administration of anticoagulation therapy
Procedure	
 - ACT and administration of anticoagulation therapy - Model and serial number of devices used (whether or not implanted) - Number of devices implanted (if implant unsuccessful, reason for unsuccessful implant) - Procedure and Device times - Length of stay in ICU/CCU/PACU post-procedure

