15.1 Anticipated Clinical Benefits

15.2 Foreseeable Adverse Events and Anticipated Adverse Device Effects

Per the MitraClip System IFU, the anticipated events on **Table 15-1** have been identified as possible.

Table 15-1: Potential Complications and Adverse Events (MitraClip System IFU)

Allergic reaction (anesthetic, contrast, Heparin, nickel alloy, latex)	Hemorrhage requiring transfusion
Aneurysm or pseudo-aneurysm	Hypotension / hypertension
Arrhythmias	Infection
Atrial fibrillation	Lymphatic complications
Atrial septal defect requiring intervention	Mesenteric ischemia
Arterio-venous fistula	Mitral stenosis
Bleeding	Mitral valve injury
Cardiac arrest	MitraClip Implant erosion, migration or malposition
Cardiac perforation	MitraClip Implant thrombosis
Cardiac tamponade / Pericardial Effusion	MitraClip System component(s) embolization
Chordal entanglement/rupture	Multi-system organ failure
Coagulopathy	Myocardial infarction
Conversion to standard valve surgery	Nausea/vomiting
Death	Pain
Deep venous thrombus (DVT)	Peripheral ischemia
Dislodgement of previously implanted devices	Prolonged angina
Dizziness	Prolonged ventilation
Drug reaction to anti-platelet / anticoagulation agents / contrast media	Pulmonary congestion
Dyskinesia	Pulmonary thrombo-embolism
Dyspnea	Renal insufficiency or failure
Edema	Respiratory failure / atelectasis / pneumonia
Emboli (air, thrombus, MitraClip Implant)	Septicemia
Emergency cardiac surgery	Shock, Anaphylactic or Cardiogenic
Endocarditis	Single leaflet device attachment (SLDA)
Esophageal irritation	Skin injury or tissue changes due to exposure to ionizing radiation
Esophageal perforation or stricture	Stroke or transient ischemic attack (TIA)
Failure to deliver MitraClip to the intended site	Urinary tract infection
Failure to retrieve MitraClip System components	Vascular trauma, dissection or occlusion
Fever or hyperthermia	Vessel spasm
Gastrointestinal bleeding or infarct	Vessel perforation or laceration
Hematoma	Worsening heart failure
Hemolysis	Worsening mitral regurgitation
	Wound dehiscence

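### SAP 3.2 specifies no summary for adverse events judged unrelated to the device, unless they are COVID-19 events or endpoint events

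*SAP*

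**What the plan says.** On collection, Protocol 7.3.1 states: "All adverse events will be collected on each subject through the femoral vein puncture for transseptal access", continuing to the 1-year visit. Protocol 7.1.1 and Appendix II define an AE without regard to device relationship, and Appendix II expressly includes events related to the procedures.

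On attribution, Protocol 7.2 gives the investigator one question: "Determination of whether there is a reasonable possibility that a product or device caused or contributed to an AE". Protocol 11.3 likewise asks for source documentation of device relationship for serious AEs.

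On reporting, SAP 3.2 says: "All the adverse device effects, serious adverse device effects, UADEs, USADEs will be summarized for all subjects who enrolled in this trial". It adds only COVID-19 related AEs. No text in that section is blacked out. SAP 2.2 says in general terms that clinical and safety event data will be summarized, without naming classes of AE.

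On who is counted, Protocol 5.4 states: "The subject is considered to be enrolled in the study upon signing and dating the informed consent form". Registration comes later, at femoral vein puncture. Protocol 7.3.1 adds: "Adverse events will not be collected for screen failure subjects". Protocol 11.4 adds: "eCRF data will be collected for all subjects who are registered into the study".

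**The concern.** The study exists to confirm safety and efficacy in Chinese patients in a report to the regulator (Protocol 1.1.2 and 2.1). If the AE tables are limited to device effects, a site's answer to one attribution question decides whether a non-endpoint event is tabulated at all. Protocol 3.2 lists an echocardiography core laboratory among the bias controls but no event adjudication, so nothing in the visible plan checks that answer.

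The events most exposed are harms from parts of the procedure other than the clip and its catheters. A reader of the report would reasonably expect to see these, and the protocol itself foresees them.

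**Working it through.** No figure in the plan needs reproducing. The check compares what is collected with what is specified for summary.

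**1. Collected.** All AEs in registered subjects, from puncture to 1 year (Protocol 7.3.1).

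**2. Specified for summary.**
- SAP 3.2: adverse device effects, serious adverse device effects, UADEs, USADEs and COVID-19 AEs.
- SAP 1.4.1 and 2.3.1: 30-day MAE, which counts all-cause death, stroke, MI and renal failure, plus non-elective cardiovascular surgery for device or procedure related events.
- SAP 1.4.2 and 2.3.2: all-cause mortality, MAE components, major bleeding, mitral valve surgery, further MitraClip intervention, hospitalizations by reason, and a composite of device complications.

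**3. Remainder.** AEs and serious AEs that are not device-related, not COVID-19 related and not endpoint events. Only the general sentence in SAP 2.2 reaches them.

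**4. The remainder contains foreseen events.** Protocol 6.3 prepares subjects by "standard practice for a percutaneous procedure, general anesthesia, and TEE". The device listed in Appendix V consists of two clip delivery system models and the guide catheter; the TEE probe and anesthesia are not part of it. Table 15-1 (Protocol 15.2) lists "Esophageal perforation or stricture", allergic reaction to anesthetic, and prolonged ventilation. Suppose a probe injury occurs during the index stay, without major bleeding, and the investigator answers no to the device question. It is not an MAE component, not a new hospitalization and not a device effect. It may lengthen the stay, which is summarized as a duration, but the event has no table. The same holds for an arteriovenous fistula, deep vein thrombosis or access-site infection attributed to access. Appendix II defines major vascular complication and gastrointestinal complication as results of the procedure, but neither is a listed endpoint.

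**5. Size of one event.** The number of such events cannot be derived, so no rate is assumed. With 50 to 100 registered subjects and exact (Clopper-Pearson) 95% limits:
- 1/50 = 2.0% (0.05% to 10.65%)
- 1/100 = 1.0% (0.03% to 5.45%)

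An absent line is not a reported zero. If a reader took it as one, the upper limit would be 1 − 0.025^(1/50) = 7.1%, or 1 − 0.025^(1/100) = 3.6%. This is illustration, not a prediction.

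**6. Denominator, read literally.** Let N be registered subjects and S screen failures. S is not given; 5 to 20 is assumed. Each subject percentage is multiplied by N/(N + S).
- N = 50: 50/55 = 0.91 to 50/70 = 0.71, so one subject reads 1.8% to 1.4% instead of 2.0%.
- N = 100: 100/105 = 0.95 to 100/120 = 0.83, so one subject reads 0.95% to 0.83% instead of 1.0%.

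**7. Procedure relationship.** Protocol 4.1 needs it for the surgery component of MAE. The Appendix II heading for that component covers procedure and device, but the body text beneath it speaks only of device related complications.

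**The case against.** The strongest reply is that most serious harm is captured anyway. Death, stroke, MI, renal failure, major bleeding, mitral valve surgery and hospitalizations are summarized whatever the device attribution, and surgery for procedure related events counts toward MAE. A reader might infer from SAP 3.2 that all events judged not device-related, including all procedural harm, go unreported. The documents do not support that, and this part of the reply stands in full.

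Second, adverse device effect is not defined in the visible text. Protocol 15.2 lists the procedural events under a heading that includes anticipated adverse device effects, the guide catheter is a study device, and the 7.2 test is a low bar. Many access-site events would therefore be called device effects. That also stands, but without a definition the plan does not ensure it.

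Third, the table mockups mentioned in SAP 2.2.1 and the SAP appendices are not shown, and parts of SAP 2.2 and 2.3 are blacked out. A fuller table may exist. SAP 3.2, however, is the section that names the AE classes, and it is complete.

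Fourth, serious AEs go to the sponsor, ethics committee and regulator within 24 hours (Protocol 7.3.1). This protects patients, but individual case reports do not give rates in the study report.

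Fifth, *enrolled* may be loose wording: Protocol 5.1 uses it for treated subjects, and eCRF data exist only for registered ones. This largely stands, so real dilution is unlikely.

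**Conclusion.** The point holds in a limited form. AEs and serious AEs that are judged not device-related, are not COVID-19 related and are not endpoint events have no specified summary beyond the general sentence in SAP 2.2, and whether they are tabulated rests on investigator attribution. For a study meant to confirm safety, this should be corrected.

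The number of events affected is unknown; each affected subject is 1% to 2% of the registered population. The conclusion assumes that SAP 3.2 is followed as written and that some procedural events are judged not device-related.

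The denominator matter is mainly a conflict of wording between SAP 3.2 and Protocol 5.4, 7.3.1 and 11.4; the dilution factors depend on an assumed screen-failure count. It would also be tempting to say that procedure relationship is not recorded. That is only an inference from Protocol 7.2 and 11.3, because the AE page of the eCRF is not shown.

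**What to change.** 1. Change SAP 3.2 to tabulate all AEs and all serious AEs by MedDRA term regardless of relationship, with device effects shown as a subset.
2. In SAP 3.2, replace enrolled with registered subjects as the denominator.
3. Minor: if the eCRF does not already do so, record procedure relationship beside device relationship, and say so in Protocol 7.2.
4. Minor: align the body text of the surgery definition in Appendix II with its own heading and with Protocol 4.1, so that it covers device or procedure related events.

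The cost is SAP and protocol wording, at most one eCRF field, and fuller tables from AE data that sites already report. The downside is longer tables that include events unrelated to the device.

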3.3 Subject Early Termination

Subject early termination reasons including deaths, withdrawals, lost-to-follow-up, etc. will be summarized by treatment arms at all scheduled visits.

3.4 Protocol Deviation

Protocol deviations will be summarized for subjects in whom a protocol deviation was reported. COVID-19 related protocol deviations will also be summarized.

4.0 DOCUMENTATION AND OTHER CONSIDERATIONS

All analyses will be performed using SAS® for Windows, version 9.3 or higher.

Statistical Analysis Plan

5.0 ACRONYMS AND ABBREVIATIONS

Acronym or Abbreviation	Complete Phrase or Definition
6MWD	Acute procedural success
AP	Attempted Procedure Population
APS	Acute Procedure Success
CCU	Critical Care Unit
CI	Cardiac Index
CO	Cardiac Output
DMR	Degenerative Mitral Regurgitation
ECL	Echocardiographic Core Laboratory
FMR	Functional Mitral Regurgitation
FSV	Forward Stroke Volume
GEE	Generalized Estimating Equation
HRR	High Risk Registry
ICU	Intensive Care Unit
IP	Implanted Population
FAS	Full Analysis Set
KCCQ	Kansas City Cardiomyopathy Questionnaire
LVEDD	Left Ventricular End Diastolic Dimension
LVEDV	Left Ventricular End Diastolic Volume
LVEF	Left Ventricular Ejection Fraction
LVESD	Left Ventricular End Systolic Dimension
LVESV	Left Ventricular End Systolic Volume
LVIDs	Left Ventricular Internal Dimension Systole
MAE	Major Adverse Event
MR	Mitral Regurgitation
MVA	Mitral Valve Area
MVG	Mitral Valve Pressure Gradient
NYHA	New York Heart Association
NMPA	National Medical Products Administration
QoL	Quality of Life
RF	Regurgitation Fraction
RR	Ratio of Rate
RV	Regurgitation Volume
RVSP	Right Ventricular Systolic Pressure

Statistical Analysis Plan

Acronym or Abbreviation	Complete Phrase or Definition
SAP	Statistical Analysis Plan
SLDA	Single Leaflet Device Attachment
TEE	Transesophageal Echocardiogram

7.0 APPENDICES

Statistical Analysis Plan
